#### **5.4.1 Data Collection and Follow-up for Withdrawn Subjects**

Subjects who choose to withdraw from the study or will be withdrawn from the study at the discretion of the PI or co-I will not require any additional follow-up data collection for this study.

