## 4 Study Population and Duration of Participation

### 4.1 Duration of Study Participation

The subject's participation in this study will be limited to the time of their upper airway surgery and the time needed for post-operative recovery. No long-term follow-up will be conducted for this study.

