### **5.4 Subject Withdrawal**

All study subjects may withdraw from the study at any time without impact to their care. They may also be discontinued from the study at the discretion of the PI and co-Is if it is determined that they are not good candidates for Hi-VNI use immediately prior to surgical procedure or during the surgical procedure. This decision will be made based on a joint discussion between the airway surgeon and the anesthesiologist.

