### **7.3 Recording of Adverse Events**

All adverse events occurring during the study period will be recorded. The clinical course of each event will be followed until resolution, stabilization, or until it has been determined that the study intervention or participation is not the cause. Serious adverse events that are still ongoing at the end of the study period will be followed up to determine the final outcome. Any serious adverse event that occurs after the study period and is considered to be possibly related to the study intervention or study participation will be recorded and reported.

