### **10.1 Risks**

All subjects included in this study will be informed about potential risks associated with the use of the Hi-VNI device during surgery based on the previously published studies and the safety information reported by the Hi-VNI device manufacturer. These risks include nasal discomfort and/or rhinorrhea. To our knowledge, no other risks have been previously directly linked to Hi-VNI use. These side effects of Hi-VNI use could be related to dry nasal mucosa after use of high-flow nasal insufflation, and will prescribe nasal saline sprays and recommend Tylenol or other mild over the counter analgesics in cases when patients report symptoms of nasal pain and/or rhinorrhea.

To minimize the risk of inadequate oxygenation and other complications, careful continuous monitoring will be maintained throughout the case. All patients will receive preoxygenation with a bag-mask to ensure that mask ventilation can be performed successfully during the case if needed and to determine the baseline gradient between end-tidal CO2 and TcpCO2. If mask ventilation during the induction phase is unsuccessful, the anesthesia team will intubate the patient or HFJV will be initiated after exposure of the glottis by the airway surgeon, and the patient will be withdrawn from the study.

The Hi-VNI device will be used during the surgical procedure with continuous monitoring by anesthesia team. If at any point the SpO2 drops below 90% or the value of TcpCO2 minus the baseline gradient rises above 55 mmHg, the airway surgeon and the anesthesiologist will stop the procedure and will switch to an alternate means of oxygenation immediately by placing an HFJV cannula or a small sized endotracheal tube through the laryngoscope into the glottis/trachea (a step performed in the beginning of the case if HFJV or endotracheal intubation are selected as primary methods of oxygenation during the case). Continuous monitoring in the OR will help us avoid TcpCO2 minus the baseline gradient levels above 55 mmHg (levels of TcpCO2 not previously correlated clinically with PaCO2). As soon as this threshold value is reached, the surgeon will place an endotracheal tube through the

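### Section 5.4.1 waives further data for subjects whom investigators withdraw, possibly after Hi-VNI has started, with no safety exception, and so conflicts with sections 7.1.1, 7.3 and 7.5.1

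*Combined protocol and SAP*

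**What the plan says.** Section 5.4 allows the investigators to discontinue a subject if they judge that "they are not good candidates for Hi-VNI use immediately prior to surgical procedure or during the surgical procedure". The surgeon and the anesthesiologist decide this together.

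Section 5.4.1 covers both subjects who leave by their own choice and those whom an investigator removes. It says that they "will not require any additional follow-up data collection for this study". It makes no exception for adverse events or for subjects already exposed to the device.

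The safety sections set other duties. Section 7.3 has all adverse events in the study period recorded and adds: "The clinical course of each event will be followed until resolution, stabilization", or until the study has been ruled out as the cause. Section 7.5.1 makes the investigator responsible for following every serious event until it resolves or is stable. Section 7.1.1 lists leading to study withdrawal among the features that turn an abnormal diagnostic result into an adverse event. None of the three exempts withdrawn subjects.

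Section 3.3 plans a post-operative assessment of each participant, covering airway complications and prolonged drowsiness.

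**The concern.** The discretionary rule in 5.4 reaches into the operation itself. A subject can therefore have received Hi-VNI, be judged unsuitable part-way through, and be withdrawn. From then on 5.4.1 releases the study team from collecting anything more, just before the recovery-unit assessment would be made. Sections 7.3 and 7.5.1 still require that subject's events to be recorded and followed.

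At stake is the safety description of an exposed group. If 5.4.1 is applied, events in subjects withdrawn mid-case may go unrecorded, or be recorded without an outcome, and the reported counts would be too low. The decision to withdraw (5.4), the causality judgment (7.4) and the safety monitoring (7.5.2) all rest with the investigators, and there is no monitoring committee, so no independent body is placed to notice such a gap.

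This point is about safety follow-up only. How withdrawn subjects count in the completion rate is a separate question.

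**Working it through.** The protocol states no figure on this point, so the check is a reading of its sections against one another.

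1. **Can an exposed subject be withdrawn by an investigator?** Yes. Under 3.3, Hi-VNI starts after induction and a successful trial of mask ventilation. Section 5.4 allows discontinuation before or during surgery, so the second case includes time on Hi-VNI.

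2. **What does 5.4.1 then require?** No further follow-up data, whatever the reason for withdrawal.

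3. **What do the safety sections require for the same subject?** Recording of all events in the study period and follow-up of each to an end point (7.3), and follow-up of serious events (7.5.1).

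4. **Where do the rules collide most clearly?** Take a subject withdrawn because of an abnormal diagnostic result. By 7.1.1 that result is an adverse event. By 7.3 it must be followed. By 5.4.1 no further data are needed. The withdrawal that makes the result an adverse event also triggers the waiver.

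5. **Which subjects are affected?**
   - Failed mask ventilation at induction leads to removal from the study (3.3, 10.1), but before Hi-VNI is used. These subjects are not exposed.
   - Low saturation or a raised corrected transcutaneous CO2 leads to a switch of oxygenation method (3.3, 10.1). This is not described as withdrawal, and under 3.4.1 such a case is a failure on the primary endpoint. These subjects appear to stay in the study.
   - What remains is the discretionary group in 5.4. Nothing there separates it from rescue, so a subject who is doing poorly could be handled under either rule.

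6. **How large could the effect be?** The protocol gives neither a withdrawal rate nor an event rate. As an illustration on assumed values only, let 5 to 20 of the 100 planned subjects (4.2) be withdrawn after exposure, with an event rate of 5% in retained subjects and 10% to 30% in withdrawn subjects, and let no event in a withdrawn subject be captured.
   - True rate = [w × p_w + (100 − w) × 0.05] / 100.
   - Smallest case, w = 5 and p_w = 0.10: (0.5 + 4.75)/100 = 5.25%.
   - Largest case, w = 20 and p_w = 0.30: (6 + 4)/100 = 10.0%.
   - The rate seen among retained subjects would be 5.0% throughout. Recorded events over all 100 would be 4.75% when w = 5 and 4.0% when w = 20.

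   This shows the direction of the error and how it depends on the inputs. It is not an estimate for this trial.

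**The case against.** The best defense is that 5.4.1 says only that further data are not needed. It does not forbid collecting them. Sections 7.3 and 7.5.1 exempt nobody, and 7.1.1 brings an abnormal result that causes withdrawal within 7.3. A careful team would read the safety sections as prevailing. This stands in part: the protocol supports a risk of lost events and does not show that events will be lost. But 5.4.1 is the specific rule on withdrawn subjects, and staff would naturally apply it.

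A reader might infer that the withdrawn subjects are those most likely to have events. The protocol does not support that. Subjects with desaturation, hypercarbia, arrhythmia, hypotension treated with a vasopressor, or bleeding that needs cautery are switched or intubated, and no section calls this withdrawal. Neither the size nor the risk of the discretionary group is given.

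A reader might also infer that 4.1 and 5.2 contradict 7.3. Section 4.1 says that participation is "limited to the time of their upper airway surgery and the time needed for post-operative recovery" and that "No long-term follow-up will be conducted for this study", while 7.3 says: "Any serious adverse event that occurs after the study period and is considered to be possibly related" to the study is to be recorded and reported. These can coexist, as a scheduled collection window and a separate safety duty. What is missing is a described means of detecting late events, and there is some tension over non-serious events still open at discharge. Nor would detection be left wholly to chance: the principal investigator is the subjects' own surgeon (4.5), and the electronic record is a primary data source (8.2). The schedule of events in 3.3 has no readable content in the text at hand, so a later check cannot be excluded.

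Finally, 10.1 says that the team "will prescribe nasal saline sprays and recommend Tylenol or other mild over the counter analgesics in cases when patients report symptoms". It is tempting to conclude that device symptoms outlast the recovery unit, but the section does not say when patients would report them.

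**Conclusion.** The point holds for 5.4.1. As written, its waiver cannot be squared with 7.1.1, 7.3 and 7.5.1 for a subject withdrawn by an investigator after Hi-VNI has started. The likely direction is under-reporting of events in exposed subjects. This rests on two assumptions: that some discretionary withdrawals occur after exposure, and that staff follow 5.4.1 literally.

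The size cannot be computed from the protocol. A bound based on zero observed events would not supply it. The exact two-sided 95% upper limit, 1 − 0.025^(1/n), is 3.6% for 0 of 100 and 4.0% for 0 of 90, but the 10 missing subjects behind the second figure are an assumption, and an adverse event rate is not among the endpoints in 3.4.

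Sections 4.1 and 5.2 belong here only as a missing mechanism for finding later related serious events. The inconsistency in 5.4.1 should be corrected, and correcting it is cheap.

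**What to change.** - Amend 5.4.1: any subject in whom Hi-VNI was started, and whom an investigator withdraws, stays in safety data collection. This covers intra-operative events, the recovery-unit assessment, and event follow-up under 7.3 and 7.5.1. Only the subject's own withdrawal of permission ends it.
- State in 5.4 that a switch to another oxygenation method is not in itself a withdrawal. This settles study status only and leaves clinical management untouched.
- Report safety for all exposed subjects, including those withdrawn.

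The cost is protocol wording, with matching consent wording where needed, and slightly more data entry. The reported event count may rise.

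Optional: add to 4.1 and 5.2 one check of the electronic record after discharge, so that the later related serious events covered by 7.3 can be found. It would take a few minutes per subject. It is a design addition, and the correction of 5.4.1 does not depend on it.

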### **5.5 Efficacy Evaluation**

The ability of the Hi-VNI device to provide adequate oxygenation has already been demonstrated based on existing literature and a small number of cases performed at our institution. However, further evaluation of the efficacy for this oxygenation technique during upper airway surgery is one of the primary objectives for this study. All information captured during this study will contribute to our present knowledge about the ideal clinical cases and patient characteristics when Hi-VNI should be selected for upper airway procedures performed under general anesthesia.

## **6 Statistical Plan**

### **6.1 Sample Size and Power Determination**

The subjects will be recruited prospectively based on the eligibility criteria for this study. The investigators anticipate that 100 subjects will be recruited for this study between January 2020 and January 2021. This sample size is determined based on the previously noted caseload for our practice and the fact that this study duration will be limited to one year only. No comparison or control group will be used for this study. The calculation of statistical power will not be required. Patel et al showed that a rate of rise in pCO2 was 0.15 kPa/min with Hi-VNI oxygenation while measuring end tidal CO2 transcutaneously, which translates into 1.125 mmHg/min. Another study by Gustaffson et al cited average apnea duration during elective

laryngeal surgery of  $22.5 \pm 4.5$  min. Based on these values of the rate of rise for pCO2 and the average apnea duration for elective laryngeal surgery, assuming normal data distribution, the range of TcpCO2 change for procedure length within one standard deviation of the mean value (22.5 min) will be [20.25; 30.38].

Using a normal end-tidal CO2 value of 37.5 mmHg and adding this value to the limits of the range of change in TcpCO2 listed above will give us a range of the values for TcpCO2 at the end of the procedure assuming the average duration of the procedure is  $22.5 \pm 4.5$  min. This range of the TcpCO2 at the end of the procedure would be [57.75; 67.88]. Our cutoff of TcpCO2 minus the baseline gradient between TcpCO2 and end-tidal CO2  $> 55$  mmHg is when the mode of oxygenation will be changed from Hi-VNI to an alternate method (endotracheal intubation or HFJV). The baseline gradient will be measured as the TcpCO2 minus the end-tidal CO2 during routine pre-oxygenation with a facemask. Based on the normal distribution assumption, one can deduce that only procedures with the duration one standard deviation away from the mean duration value of 22.5 min will not reach this level of TcpCO2. In other words, approximately 16% of patients will not require alternate means of ventilation (population which falls to the left of the line through a value of (22.5-4.5) on the normal distribution curve or 15.85%). Based on the author's prior experience and operative volume, there are 2-3 elective cases per week performed by the PIs that may qualify based on the inclusion/exclusion criteria to be included in the study. If 3 cases per week is used will equal to 144 qualified cases per year. For the confidence interval of 95% and the margin of error of 5% with the rate of 16%, the calculated sample size will equal to 86 individuals who might have a good chance of having their procedure completed with Hi-VNI without a need to switch to alternate mode of oxygenation. To account for the fact that some patients may not consent to be in the study or may require alternate means of oxygenation after Hi-VNI is used for other reasons, we added 14 patients to the sample size. This would lead to an estimated sample size of 100 individuals.

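### Section 6.1 expects 16% of cases to finish on Hi-VNI alone, but its own inputs reach the 55 mmHg switch limit at 15.56 min, not 18 min, and give 6.1%

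*Combined protocol and SAP*

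**What the plan says.** Section 6.1 (Sample Size and Power Determination) builds the expected completion rate in four steps.

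1. A published CO2 rise of 0.15 kPa/min is converted, "which translates into 1.125 mmHg/min". A second study is "cited average apnea duration during elective" laryngeal surgery, 22.5 ± 4.5 min, with normality assumed.
2. Adding the rise over 18 and 27 min to a normal end-tidal value of 37.5 mmHg, the section states that TcpCO2 "at the end of the procedure would be [57.75; 67.88"] mmHg.
3. It recalls the switch limit (TcpCO2 minus the baseline gradient above 55 mmHg) and concludes that "only procedures with the duration one standard deviation away from the mean duration value of 22.5 min will not reach this level of" TcpCO2. From the area left of 22.5 − 4.5 min it deduces that "approximately 16% of patients will not require alternate means of ventilation".
4. That rate enters a precision calculation: for 95% confidence and "the margin of error of 5% with the rate of 16%, the calculated sample size will equal to 86 individuals". Just before this, the caseload at three cases a week is said to be such that it "will equal to 144 qualified cases per year". Fourteen patients are added because "some patients may not consent to be in the study or may require alternate means of oxygenation after Hi-VNI is used for other reasons", giving 100.

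Section 3.4.1 makes completion without another mode of oxygenation the primary endpoint. Section 3.1 plans to describe the best clinical scenarios from the cases completed that way.

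**The concern.** Steps 2 and 3 contradict each other. The projection at 18 min, 57.75 mmHg, is 2.75 mmHg above the 55 mmHg limit, yet cases lasting up to 18 min are counted as never reaching it. The cut point was set at one standard deviation below the mean duration. It should be the time at which projected CO2 meets the limit.

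The 16% is the only planning figure for the primary endpoint and a direct input to the 86. It also suggests how many completed cases will be available for the Section 3.1 aim. If the plan's inputs imply far fewer, investigators and the IRB should see that number.

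**Working it through.** **Inputs, all from Section 6.1:** start 37.5 mmHg; rise 1.125 mmHg/min; duration normal with mean 22.5 and SD 4.5 min; limit 55 mmHg (also in Section 3.3); 95% confidence; margin 5 points; 144 cases a year. Because the projection starts from an end-tidal value, it is already on the gradient-corrected scale, and the 55 mmHg limit applies to it directly.

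**The plan's own figures reproduce.**
- CO2 at 18 min: 37.5 + 18 × 1.125 = 57.75. At 27 min: 37.5 + 27 × 1.125 = 67.88.
- P(duration < 18) = Φ((18 − 22.5)/4.5) = Φ(−1) = 15.9%, the stated 16%.
- Uncorrected sample size: n0 = 1.96² × 0.16 × 0.84 / 0.05² = 206.5, so 207. With a finite-population correction to 144: 206.5 / (1 + 205.5/144) = 85.1, so 86. The 86 therefore depends on a correction that the section does not name.

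**Corrected rate.**
- Time to the limit: (55 − 37.5)/1.125 = 15.56 min.
- z = (15.56 − 22.5)/4.5 = −1.543, so P(duration < 15.56) = 6.1%.
- Per 100 patients: about 6 completers, not 16.

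**What would rescue 16%?** With the stated duration held fixed, 18 min is the right cut point only if the rise is 17.5/18 = 0.97 mmHg/min or the start is 55 − 18 × 1.125 = 34.75 mmHg. The plan states neither. The later ETCO2 limit of 60 mmHg does not help: it is reached at 20 min and gives 28.9%, and by then the tube is already in place.

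**Consequence for sample size and precision.** At p = 0.0614, n0 = 88.5 (89), or 55.1 (56) with the correction to 144. The 95% margins, 1.96 × √(p(1 − p)/n), without correction are:

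| n | p = 6.1% | p = 16% | p = 50% |
|---|---|---|---|
| 100 | 4.7 points | 7.2 | 9.8 |
| 86 (assumed analysable) | 5.1 | 7.7 | 10.6 |

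The Wilson 95% interval for 6/100 is 2.8% to 12.5%.

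**Sensitivity (assumed values, not in the plan).**

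| Rise, mmHg/min | Limit reached, min | Completion |
|---|---|---|
| 0.75 | 23.33 | 57% |
| 0.9 | 19.44 | 25% |
| 1.0 | 17.5 | 13% |
| 1.125 (plan) | 15.56 | 6.1% |
| 1.25 | 14.0 | 2.9% |

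With the plan's rise, a start of 35 to 40 mmHg gives 14.7% to 2.1%. If 5% to 20% of the cases finishing under the CO2 limit switched for another cause, 6.1% would fall to 5.8% (0.0614 × 0.95) to 4.9% (0.0614 × 0.80).

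**The case against.** The arithmetic is not in dispute; the case on the other side is that it hardly matters and that 6% may be no better a forecast.

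- **Little depends on it.** Section 6.1 also sets the sample by caseload and a one-year limit and says no power calculation is needed. There is no comparator and no success threshold, and Section 6.3.2 analyses the primary outcome descriptively. The error even asks for more patients than the corrected rate does (86 against 56, or 207 against 89). This stands, and it is why the consequence is small.
- **Duration could restore 16%.** With SD 4.5, a mean near 20 min gives about 16% below 15.56 min, and Section 3.3 expects most cases to finish within 20 min. But that clock starts at the surgeon's first step, whereas Hi-VNI starts earlier, after induction, and Section 6.1 explicitly uses 22.5 min. This does not repair the derivation. It does show that the forecast is uncertain and that one clock start should be named. The 20-minute blood-sample trigger in Section 3.3 is already counted from Hi-VNI use.
- **6% is fragile too.** The rise and duration are borrowed from other studies. This trial uses no muscle relaxation and includes spontaneously breathing patients (Sections 3.3 and 2.1), so the true rate could be quite different. This stands as a reason to present 6% as conditional. It does not defend 16%, which the plan presents as deduced from its stated inputs.
- **The 5-point margin is a normal approximation.** The Wilson interval for 6/100 extends 6.5 points above the estimate (12.5 − 6). That is fair, and a reason to report the Wilson interval.

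**Conclusion.** The concern holds: Section 6.1 is wrong as written, with minor consequence. Its inputs give a completion rate of 6.1%, and the stated 16% is about 2.6 times that (15.9/6.1). Roughly 10 in every 100 patients, those with durations between 15.56 and 18 min, are counted as completers although the model has them switched.

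The 6.1% rests on a linear rise of 1.125 mmHg/min from 37.5 mmHg, a normal duration of 22.5 ± 4.5 min, and CO2 as the only reason to switch. It is what the plan implies, not a prediction of what will be observed. The sample of 100 does not need to change. What does change is the expected number of completed cases behind the Section 3.1 description: about 6, not 16. The unnamed finite-population correction and the differing clock starts are points to clarify, not errors.

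**What to change.** In Section 6.1 replace 18 min, 16% and 86 with 15.6 min, about 6% and 56 (89 uncorrected), and justify 100 by caseload. Suggested text:

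> At 37.5 mmHg and 1.125 mmHg/min the 55 mmHg limit is reached at 15.6 min. With a normal duration of 22.5 SD 4.5 min, counted from [start of Hi-VNI], about 6% of cases would finish before it. This rate depends on the assumed rise rate and duration and counts only CO2-triggered switches. A 5-point margin then needs 89 patients (56 with finite-population correction to 144 cases). The sample of 100 is set by caseload; its 95% margin without correction is 4.7 points at 6%, 7.2 at 16% and 9.8 at 50%.

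Claim the uncorrected margin, report the observed rate with a Wilson interval, and use the same clock start in Section 3.3. If the investigators believe another rise rate or duration is more realistic for this population, they should state it and recompute from it.

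The cost is a recalculation, a few sentences and one clock definition. The sample size, procedures, switch limits and planned analysis stay as they are. The expected completion rate on record becomes lower.

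### Section 6.1 counts every case under 18 minutes (about 16%) as staying below the 55 mmHg switch limit, but its own projection puts an 18-minute case at 57.75 mmHg; the quoted inputs imply 6.1%

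*Combined protocol and SAP*

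**What the plan says.** The primary endpoint (section 3.4.1) is completion of the case on Hi-VNI alone. Section 6.1 derives a planning rate for it in four steps.

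- It takes a published CO2 rise of 0.15 kPa/min, "which translates into 1.125 mmHg/min", and a published apnea duration of 22.5 ± 4.5 min.
- It adds the rise over 18 and 27 min to a normal end-tidal value of 37.5 mmHg. The projected TcpCO2 "at the end of the procedure would be [57.75; 67.88" mmHg.
- It restates the switch limit: TcpCO2 minus the baseline gradient above 55 mmHg. It then says that "only procedures with the duration one standard deviation away from the mean duration value of 22.5 min will not reach this level".
- It converts this into a rate, "In other words, approximately 16% of patients will not require alternate means of ventilation", which it identifies as the "population which falls to the left of the line through a value of (22.5-4.5) on the normal distribution curve or 15.85" (per cent).

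The 16% then enters a precision calculation (95% confidence, margin of 5 points). The source population is described thus: "If 3 cases per week is used will equal to 144 qualified cases per year". The result is that "the calculated sample size will equal to 86 individuals". Fourteen are added for non-consent and for patients who "may require alternate means of oxygenation after Hi-VNI is used for other reasons", giving 100. Earlier in the same section, the 100 is said to rest on caseload and a one-year study, and a power calculation is said not to be needed.

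**The concern.** The 18-minute cut point is the mean minus one SD. It is not the time at which the 55 mmHg limit is reached. The lower end of the plan's projected range, 57.75 mmHg, belongs to that 18-minute case and lies 2.75 mmHg above the limit. Cases a little shorter than 18 min are therefore counted as staying under a limit that the plan's own model says they have passed.

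This deserves correction because 16% is the only planning value given for the primary endpoint and is the rate entered to obtain 86. As written, the rate, the projection and the limit cannot all hold together, and a reader cannot reproduce 86 without guessing a step that is not stated.

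**Working it through.** **Inputs, all from section 6.1.** Start 37.5 mmHg; rise 1.125 mmHg/min; duration Normal with mean 22.5 and SD 4.5 min; limit 55 mmHg; 95% confidence; margin 0.05; 144 cases per year.

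**1. The plan's own figures reproduce.**
- 0.15 × 7.5 = 1.125 mmHg/min.
- 37.5 + 18 × 1.125 = 57.75; 37.5 + 27 × 1.125 = 67.875. Both match.
- Φ((18 − 22.5)/4.5) = Φ(−1) = 15.87%, matching the stated 15.85%, or about 16%.

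**2. Scale check.** The gradient is defined as TcpCO2 minus end-tidal CO2 at pre-oxygenation, so gradient-adjusted TcpCO2 starts at the end-tidal value. The 37.5 is an end-tidal value. The 57.75 and the 55 are therefore on the same scale, and the gradient does not explain the gap.

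**3. Crossing time and implied rate.**
- (55 − 37.5)/1.125 = 17.5/1.125 = 15.56 min.
- (15.56 − 22.5)/4.5 = −1.543, and Φ(−1.543) = 6.1%.
- Cases lasting 15.56 to 18 min: 15.87% − 6.14% = 9.7%. These are the cases wrongly counted as staying below the limit.
- For 18 min to be the crossing time, the model would need a limit of 57.75 mmHg, or a start of 55 − 20.25 = 34.75 mmHg, or a rise of 17.5/18 = 0.972 mmHg/min. Section 6.1 states none of these.

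**4. Calculated N.** n0 = 1.96² × p(1 − p)/0.05². With a finite-population correction, n = n0/(1 + (n0 − 1)/144).

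| p | n0 | corrected for 144 |
|---|---|---|
| 16% | 206.5 → 207 | 85.1 → 86 (the stated figure) |
| 6.1% | 88.5 → 89 | 55.1 → 56 |

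Section 6.1 names no correction. It is inferred because it reproduces 86 exactly and the uncorrected formula does not.

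**5. Precision at n = 100.** Half-width = 1.96 × √(p(1 − p)/100). The corrected half-width multiplies this by √((144 − 100)/143) = 0.555.

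| p | without correction | with correction |
|---|---|---|
| 16% | ±7.2 points | ±4.0 points |
| 6.1% | ±4.7 points | ±2.6 points |

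**6. Sensitivity of the 6.1%, one input at a time.** The alternative values are assumptions and are not in the plan.
- Start 35, 36 or 40 mmHg: 14.7%, 10.6% or 2.1%.
- Rise 1.0 or 1.25 mmHg/min: 13.3% or 2.9%.
- SD 3 or 6 min: 1.0% or 12.4%.
- Mean 20 min: Φ((15.56 − 20)/4.5) = 16.2%.

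**The case against.** **The sentence before the rate can be read as correct.** If it means only that a case staying under the limit must be more than one SD shorter than the mean, it agrees with the projected range, because every case within one SD ends above 55 mmHg. This stands. The slip comes in the next sentence, which turns a necessary condition into an estimate. That is why 16% can be kept as an upper bound under the stated inputs but not as the expected rate.

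**No decision changes.** Below 50%, a higher rate gives a larger N, so 16% was the cautious input for sizing (86 against 56). The 100 also rests on caseload, the analyses in sections 6.2 and 6.3.2 set no success criterion, and nothing is tested against 16%. This stands and fixes the weight of the point.

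**The inputs are rough, so 6.1% is no better as a planning value.** This also stands. An assumed mean of 20 min gives 16.2%, but that is coincidence and does not repair a derivation that uses 22.5 min and an 18-minute cut. Section 3.3 expects most cases to be done within 20 min of the surgeon's first step. That interval is not the apnea duration used in 6.1, so the two cannot simply be exchanged.

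**Stronger readings that the documents do not support.** A reader might infer that only about 6 of 100 cases will be completed. The model assumes continuous apnea, a constant rise and CO2 as the only reason to switch. The plan includes spontaneously breathing patients (section 2.1), uses no muscle relaxation (section 3.3) and allows switches for other reasons. A reader might also infer that the 86 is an arithmetic error or that 100 is too few. The 86 follows from 16% once the correction is applied, and the lower rate calls for fewer subjects, not more.

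**Conclusion.** The inconsistency is real and lies within one paragraph of section 6.1. On the quoted inputs the 55 mmHg limit is reached at 15.56 min, not 18 min, and the implied rate is 6.1% instead of about 16%. The 16% is at most an upper bound under those inputs. The result rests on the plan's own assumptions: linear rise from a single starting value, normally distributed duration, and CO2 as the only reason to switch. It checks the paragraph's consistency and does not predict the trial's result.

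The calculated N falls from 86 to 56 if the finite-population correction is used, or from 207 to 89 if it is not. The figures with the correction depend on the inference that it was applied. Severity is minor: the planned 100 does not become too small, and no test, success criterion, procedure or clinical limit depends on the 16%.

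**What to change.** Rewrite the justification paragraph in section 6.1 as follows.

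- Replace the one-SD cut with the crossing time, so that the rate, the projection and the 55 mmHg limit stated there are reconciled. Alternatively, keep 16% but label it an upper bound under the stated inputs. No view is taken here on the limit itself.
- Say that the rate covers the CO2 criterion only and is sensitive to the assumed start, rise and duration.
- Name the finite-population correction if it is used, and restate the calculated N with the rate that is kept.
- Give the precision at n = 100 on one stated basis. At 6.1% this is ±4.7 points without the correction or ±2.6 with it; at 16% it is ±7.2 or ±4.0. The corrected figures describe the year's 144 cases, and the uncorrected ones are for inference beyond them.

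The cost is one paragraph. The stated planning rate becomes less favourable if the quoted inputs are kept. The total of 100 can stand on caseload with its precision stated, and no procedure or clinical limit changes.
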